9.3.3 Removal of Subjects from Therapy or Assessment

The investigator may discontinue study drug or withdraw the subject from the study at any time for safety or administrative reasons. The subject may decide to stop study drug or withdraw from the study at any time for any reason.

Subjects who discontinue taking study drug prematurely for any reason will undergo an ED Visit within 7 days of their last dose of study drug (see [Section 9.1.2.2](#)). Follow-Up Visits will also be scheduled 2, 4, 8, and 12 weeks after the last dose of study drug (see [Section 9.1.2.3](#)). Subjects who discontinue study drug prematurely will also be scheduled to return to the study site for each scheduled visit when clinical efficacy assessments are to be conducted (ie, at Visits 11, 14, 15, 16, 17, and 18, if these visits have not already been performed). At these visits, only clinical efficacy assessments (MMSE, CDR, ADAS-cog₁₄, FAQ, CBB and ISLT) will be conducted. Regularly scheduled clinical efficacy visits do not need to be attended if they fall within 8 days (visit window) after the Early Discontinuation Visit or within ± 8 days of Follow-Up Visit 19 or Visit 20. Subjects who discontinue early from study drug are considered on study as long as they return for their regularly scheduled clinical efficacy visits as outlined above. (revised per Amendment 04)

The primary reason for discontinuation and all other reason(s) contributing to the subject's discontinuation from study drug(s) should be collected on the Subject Disposition eCRF page. In addition, the date of last dose of study drug(s) will be recorded on the Study Drug Dosing eCRF page. If a subject discontinues study drug and withdraws from the study at the same time, the ED Visit will be followed (see [Section 9.5.5](#)).

Safety-related criteria for discontinuation of study drug include the following:

- a. A study drug discontinuation threshold will be set based on absolute counts of CD4 (T helper cells), CD8 (cytotoxic T cells), or CD19 (B cells). The discontinuation threshold will be set at below the level of the population-adjusted LLN (CD4=396 cells/ μ L; CD8=157 cells/ μ L; and CD19=74 cells/ μ L), at a level that represents a greater risk of opportunistic infection in the treated population. (revised per Amendment 02) For CD4 (T helper cells) the discontinuation threshold is 250 cells/ μ L. For CD8 (cytotoxic T cells) and CD19 (B cells) the discontinuation thresholds are 150 cells/ μ L and 50 cells/ μ L, respectively. Any subject who has CD4 (T helper cells), CD8 (cytotoxic T cells), or CD19 (B cells) absolute counts below the discontinuation threshold as confirmed by a repeat test conducted within 1 week of the initial test but who has no clinical signs or symptoms of infection, will have study drug temporarily suspended for at least 2 weeks but no more than 4 weeks. During this period of study drug suspension, lymphocyte subset counts and complete blood count (CBC) with differentials will continue to be tested weekly until CD4 (T helper cells), CD8 (cytotoxic T cells), and CD19 (B cells) have all returned to greater than the population-adjusted LLN after which time study drug can be resumed. Testing of lymphocyte subset counts and CBC with differentials is required weekly for 4 weeks following resumption of study drug administration. Temporary suspension and rechallenge with study drug is only permitted once for any given subject. If the lymphocytes and CD counts do not return to greater than the population-adjusted LLN within 4 weeks from the start of temporary suspension the subject will need to be permanently discontinued from study drug. (revised per Amendment 04)
- b. Subjects with CD4 (T helper cells), CD8 (cytotoxic T cells), or CD19 (B cells) absolute counts between the population-adjusted LLN and the discontinuation threshold will have lymphocyte subset counts performed on a weekly basis. (revised per Amendments 02 and 04) During the early stages of the treatment period, where visits are conducted weekly (ie, Visits 4, 5, 6, and 7), lymphocyte subsets are already scheduled to be measured on a weekly basis and so additional visits or blood draws are not required. (revised per Amendment 02) For these subjects, the decision as to whether the subject remains on study drug or is to be discontinued from study drug will be based upon clinical judgment and will take into account any clinical presentation in addition to the lymphocyte subset counts. These subjects may continue with treatment if there is no clinical evidence of infection. They will be discontinued from study drug if they have infections of a moderate to severe intensity (eg, subjects whose infections are not localized, or are systemically unwell, or who require systemic anti-infective drug treatment).

Table 1 Study Drug Actions for Lymphocyte Subset Absolute Counts

| Lymphocyte subset absolute counts | Action | Decision to continue, discontinue, or temporarily suspend study drug |
|---|--|--|
| CD4 (T helper cells), CD8 (cytotoxic T cells), or CD19 (B cells) absolute counts below discontinuation threshold and no clinical signs or symptoms of infection | Retest within 1 week along with CBC with differentials | If retest performed within 1 week confirms lymphocyte subset counts below the discontinuation threshold, temporarily suspend study drug for between 2 and 4 weeks. Continue weekly testing of lymphocyte subsets and CBC with differentials. Rechallenge with study drug allowed when CD4 (T helper cells), CD8 (cytotoxic T cells), and CD19 (B cells) absolute counts all greater than population-adjusted LLN. Temporary suspension and rechallenge permitted only once for each subject. |
| CD4 (T helper cells), CD8 (cytotoxic T cells), or CD19 (B cells) absolute counts between population-adjusted LLN and discontinuation threshold | Lymphocyte subset counts (and CBC with differentials) to be performed weekly until lymphocyte subset counts return to \geq population-adjusted LLN | Decision will be based upon lymphocyte subset counts and clinical judgment |

LLN = lower limit of normal, CBC = complete blood count.

(Table revised per Amendments 02 and 04)

- c. Subjects with clinical evidence of infection will have their CD4 (T helper cells), CD8 (cytotoxic T cells), and CD19 (B cells) absolute counts measured. Blood and other biological samples will also be collected for investigations of infective pathogens (eg, serological tests, quantitative polymerase chain reaction, microscopy, and culture) where appropriate. In subjects with infection, if any of their absolute cell counts meets the discontinuation thresholds, study drug will be discontinued. All subjects with severe infections will be discontinued from study drug. All subjects with herpes zoster (shingles) or ocular herpes infections will be discontinued from study drug, regardless of severity of presentation. Subjects with mild or moderate infection may continue treatment with study drug unless otherwise clinically indicated or otherwise specified below. Specifically, when any of the CD4 (T helper cells), CD8 (cytotoxic T cells), and CD19 (B cells) absolute counts are between the population-adjusted LLN and the discontinuation thresholds, subjects with infections of moderate intensity will be discontinued from study drug (eg, subjects whose infections are not localized, or subjects who are systemically unwell, or who require systemic anti-infective drug treatment). All subjects with infection who are discontinued from study drug will be followed for a period of 12 weeks or until the infection resolves/ stabilizes or until the CD4 (T helper

cells), CD8 (cytotoxic T cells), and CD19 (B cells) absolute counts have returned to greater than population-adjusted LLN (whichever comes latest). (revised per Amendments 02 and 04)

Table 2 Study Drug Actions for Lymphocyte Subset Absolute Counts and Infection

| Criterion | Severity of Infection | | | |
|--|--|---|---|------------------------|
| | None | Mild | Moderate | Severe |
| CD4 (T helper cells), CD8 (cytotoxic T cells), or CD19 (B cells) absolute counts below discontinuation threshold | If confirmed with repeat testing within 1 week, then temporarily suspend study drug as per instructions above. | Discontinue study drug | Discontinue study drug | Discontinue study drug |
| CD4 (T helper cells), CD8 (cytotoxic T cells), or CD19 (B cells) absolute counts between population-adjusted LLN and discontinuation threshold | May continue treatment with study drug unless discontinuation is clinically indicated | May continue treatment with study drug unless discontinuation is clinically indicated | Discontinue study drug | Discontinue study drug |
| CD4 (T helper cells), CD8 (cytotoxic T cells), or CD19 (B cells) absolute counts always > population-adjusted LLN | May continue treatment with study drug unless discontinuation is clinically indicated | May continue treatment with study drug unless discontinuation is clinically indicated | May continue treatment with study drug unless discontinuation is clinically indicated (See (e) for exception) | Discontinue study drug |

LLN = lower limit of normal.

(Table revised per Amendments 02 and 04)

- d. A subject with any skin rash of moderate to severe intensity, or any rash lasting more than 72 hours regardless of severity (see (e) for exception), will be discontinued from study drug and a dermatological consult will be requested regardless of whether the rash is considered drug-related or due to other causes. For cases where the investigator suspects a drug rash, regardless of severity, the subject will be discontinued from study drug, a dermatological consult will be requested, and a skin biopsy will be performed to confirm the diagnosis. The skin rash will be treated as per standard care and will be followed up until resolution regardless of etiology or severity.
- e. Subjects who develop moderate to severe oral or genital herpes should be discontinued from study drug. Subjects who develop a mild case of oral or genital herpes may remain on study drug even if the event lasts more than 72 hours.
- f. Development of any of the following features on MRI: vasogenic edema, macrohemorrhage, an area of superficial siderosis, or a symptomatic microhemorrhage. If discontinued from study drug, subjects will undergo an ED Visit within 7 days after

discontinuation and will attend the Follow-Up Visits 2, 4, 8, and 12 weeks after the last dose of study drug. They will also undertake an Unscheduled Visit (with MRI) at approximately 4 weeks after the visit at which such MRI features were first identified. An MRI will also be performed at approximately the time of the final Follow-Up Visit (Visit 20). Additional visits for safety may be arranged if clinically indicated in the opinion of the investigator, including after 12 weeks after the last dose of study drug. At any time during the treatment period, subjects who have asymptomatic, treatment-emergent microhemorrhages as detected by MRI, but none of the features which merit discontinuation of treatment (ie, vasogenic edema, macrohemorrhage, an area of superficial siderosis, or a symptomatic treatment-emergent microhemorrhage) may continue with treatment. These subjects will have safety assessments (including MRI) at approximately 4 weeks after the visit at which such MRI features were found. They will also continue with the scheduled MRI scans. Additional unscheduled MRI scans may be arranged on an individual subject basis in discussion with the study medical monitor. (revised per Amendment 04)

- g. A postdose ECG with an average QTcF interval >500 msec from triplicate ECGs
- h. A postdose ECG with a QTcF interval increase from baseline >60 msec and a QTcF interval >450 msec as demonstrated from triplicate ECGs
- i. Any seizure (motor or non-motor)
- j. Pregnancy

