 - c. Cutaneous manifestations of immunological disease that do not require systemic immunosuppressive therapy or systemic immunomodulatory therapy need not be excluded (topical steroid treatment is permitted).
22. CD4 (T helper cells), CD8 (cytotoxic T cells), or CD19 (B cells) absolute counts below population-adjusted LLN at Screening or Baseline and confirmed by a repeat test conducted 1 week after the initial test. The population-adjusted LLN for CD4 (T helper cells), CD8 (cytotoxic T cells), and CD19 (B cells) absolute counts are 396, 157, and 74 cells/ μ L respectively. See [Appendix 5](#). (revised per Amendment 02)
 23. Ig (IgG, IgA, or IgM) levels below the LLN at Screening or Baseline, unless both the Investigator and the Medical Monitor agree that the finding is not clinically significant. The assessment of clinical significance will include, but not be limited to, evidence of clinical immunodeficiency. The discussion with the Medical Monitor should include a detailed review of medical history of infections, clinical and laboratory findings. (revised per Amendment 01)
 24. Clinically significant deviation from normal in physical examination, vital signs, or clinically laboratory tests at Screening or Baseline
 25. A prolonged QT/ corrected QT interval (QTc) interval (QTc >450 msec) at Screening or Baseline as demonstrated by average QTc interval from triplicate ECGs. A history of risk factors for torsade de pointes (eg, heart failure, hypokalemia, family history of long QT Syndrome) or the use of concomitant medications that prolong the QT/QTc interval.
 26. Any other abnormality of the ECG at Screening or Baseline (including QRS >110 msec, abnormal electrical axis, PR interval >220 msec and conduction abnormalities) considered clinically significant by the investigator
 27. Left bundle branch block at Screening or Baseline
 28. Persistent heart rate <50 or >100 beats per minute (bpm) at Screening or Baseline
 29. Persistent systolic blood pressure (BP) >165 mmHg or <90 mmHg and diastolic BP >100 mmHg or <60 mmHg at Screening
 30. History of cardiac arrhythmias. Subjects with other heart diseases (eg, ischemic heart disease, clinically significant valvular heart disease) that are not stably and adequately controlled, or uncompensated heart failure (New York Heart Association Class III and Class IV)
 31. Type 1 or Type 2 diabetes mellitus that is not well controlled

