The following AEs will require the collection of information sufficient to provide a detailed description of the event, treatment and outcome to the Medical Monitor for the study: any treatment-emergent significant laboratory abnormality; any seizures, herpes zoster infection, severe infection; any moderate to severe drug rash or any rash lasting more than 72 hours (regardless of severity); amyloid-related imaging abnormalities (vasogenic edema, macrohemorrhage, an area of superficial siderosis, or a new microhemorrhage); a "yes" answer to Type 4 or 5 suicidal ideation, or a "yes" response to any suicidal behavior on the C-SSRS.

All AEs must be followed through the final Follow-Up visit (Visit 20), or until resolution, whichever comes first. All SAEs must be followed to resolution or, if resolution is unlikely, to stabilization. (revised per Amendment 04)

Every effort must be made by the investigator to categorize each AE according to its severity and its relationship to the study treatment.

Assessing Severity of Adverse Events

AEs will be graded on a 3-point scale (mild, moderate, severe) and reported in the detail indicated on the eCRF. The definitions are as follows:

| | |
|----------|--|
| Mild | Discomfort noticed, but no disruption of normal daily activity |
| Moderate | Discomfort sufficient to reduce or affect normal daily activity |
| Severe | Incapacitating, with inability to work or to perform normal daily activity |

The criteria for assessing severity are different than those used for seriousness (see [Section 9.5.1.5.2](#) for the definition of an SAE).

Assessing Relationship to Study Treatment

Items to be considered when assessing the relationship of an AE to the study treatment are:

- Temporal relationship of the onset of the event to the initiation of the study treatment
- The course of the event, especially the effect of discontinuation of study treatment or reintroduction of study treatment, as applicable
- Whether the event is known to be associated with the study treatment or with other similar treatments
- The presence of risk factors in the study subject known to increase the occurrence of the event
- The presence of nonstudy, treatment-related factors that are known to be associated with the occurrence of the event

Classification of Causality

The relationship of each AE to the study drug will be recorded on the eCRF in response to the following question:

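### Table 2 in Protocol 9.3.3 lets study drug continue in three infection cells where criterion (c) requires a stop for herpes zoster or ocular herpes

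*Protocol*

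**What the plan says.** Section 9.3.3 of the Protocol lists the safety criteria for stopping study drug. Criterion (c) covers infection and singles out two infections: "All subjects with herpes zoster (shingles) or ocular herpes infections will be discontinued from study drug, regardless of severity of presentation". It attaches no lymphocyte-count condition to that rule.

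Table 2 follows (c) and is marked as revised per Amendments 02 and 04, so it is current text. It crosses three count rows (below the discontinuation threshold; between the population-adjusted LLN and the threshold; always above the LLN) with four columns (no infection, mild, moderate, severe). For moderate infection with counts always above the LLN, the cell reads: "May continue treatment with study drug unless discontinuation is clinically indicated (See (e) for exception". The two mild cells in the middle and bottom rows carry the same permission without a cited exception.

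The only other pointer to the text is in the no-infection column, for counts below the threshold: "If confirmed with repeat testing within 1 week, then temporarily suspend study drug as per instructions above".

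Criterion (e), the one exception the table names, begins: "Subjects who develop moderate to severe oral or genital herpes should be discontinued from study drug". It does not mention zoster or ocular herpes.

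**The concern.** A drug-action table is what site staff are likely to consult when an infection is reported. This one has no pathogen dimension, and where it does flag an exception it sends the reader to the wrong one for these two infections. Naming a herpes exception, and only one, suggests there is no other. The wording that allows drug to continue unless stopping is clinically indicated leaves to judgment what (c) makes mandatory.

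At stake is a subject with zoster or ocular herpes kept on a drug that the protocol monitors for immune effects. The protocol treats both infections as special: a history of ophthalmic shingles or of ocular HSV is exclusionary (9.3.2, criteria 17 and 18), zoster needs a detailed description to the Medical Monitor (9.5.1.5.1), and ocular herpes is always serious (9.5.1.5.2). No estimate, test or sample size is affected.

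**Working it through.** The check sets each infected cell of Table 2 against (c).

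**Cells.** 3 count rows × 3 infection grades = 9 infected cells. Under (c), all 9 should read as a stop for zoster or ocular herpes.

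| Counts | Mild | Moderate | Severe | Cells that differ from (c) |
|---|---|---|---|---|
| Below threshold | Stop | Stop | Stop | 0 of 3 |
| Between LLN and threshold | May continue | Stop | Stop | 1 of 3 |
| Always above LLN | May continue | May continue, see (e) | Stop | 2 of 3 |

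Total: 0 + 1 + 2 = 3 of 9. None of the 9 refers to (c).

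**Can these infections be graded mild?** Yes. Section 9.5.1.5.1 defines mild as "Discomfort noticed, but no disruption of normal daily activity". That is a symptom scale and takes no account of pathogen.

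**Who is in the bottom row?** Exclusion criterion 22 (9.3.2) removes subjects with CD4, CD8 or CD19 "absolute counts below population-adjusted LLN at Screening or Baseline and confirmed by a repeat test conducted 1 week after the initial test". Apart from low counts not confirmed on repeat, subjects therefore start treatment in the bottom row, which holds two of the three cells.

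**What does (d) close?** Criterion (d) stops "A subject with any skin rash of moderate to severe intensity, or any rash lasting more than 72 hours regardless of severity". Two infections × 3 cells = 6 combinations. With (c) applied, 0 of 6 are open. Reading Table 2 and (d) without (c), and assuming that zoster shows as a skin rash and ocular herpes does not:

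- moderate zoster, counts above LLN: closed by (d), 1 combination;
- mild zoster, either row: open for at most 72 hours, 2 combinations;
- ocular herpes in any of the three cells: not covered, 3 combinations.

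Check: 1 + 2 + 3 = 6.

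**Sensitivity to grading.** Criterion (c) gives as examples of moderate infection one that is not localized, "or subjects who are systemically unwell, or who require systemic anti-infective drug treatment". If needing such treatment makes an infection moderate in every row, the two mild cells fall away for treated cases and 3 − 2 = 1 cell is left (moderate, counts always above LLN). The example is written for counts between LLN and threshold. Applied to that row only, one mild cell falls away and 3 − 1 = 2 are left. The gap is thus 1 to 3 cells, depending on how grading is read.

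**The case against.** The best reply is that the protocol as a whole gives one answer. Criterion (c) is specific and mandatory, it stands immediately above the table, and a specific rule overrides a general grid. The table sorts by count and severity and does not claim to sort by pathogen; its two pointers show that it is meant to be read with the lettered criteria. No cell orders drug to continue. On this view only a cross-reference is missing, and the cell count measures layout rather than risk.

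There are also several safeguards. Known prior ocular disease is excluded at entry. Subjects are asked at each visit about new lesions, including the conjunctiva (9.5.1.5.8), and visual disturbance leads to an ophthalmic examination (9.5.1.5.13). Section 9.2.6 names shingles among the reasons to stop. Ocular herpes is always serious and must be reported within 24 hours (9.5.4.1).

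Most of this stands: (c) governs, a site that reads both will act correctly, and the practical risk is small. It does not remove the discrepancy. Apart from 9.2.6, which names shingles but not ocular herpes, these safeguards screen, detect or report; they do not tell the site to stop drug. The table does mark exceptions where it sees them, and it marks the wrong one here. Of the drug-action rules in (c), the zoster and ocular herpes rule is the only one the table does not carry over.

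**Conclusion.** The concern holds. Table 2 is wrong as written for these two infections, in 3 of its 9 infected cells; criterion (c) is right and governs. It is a minor inconsistency, but it sits in a safety instruction. The exposure that remains is mainly mild or moderate ocular herpes and mild zoster in its first 72 hours, and only where a site takes the action from the table without (c). This rests on the general severity scale in 9.5.1.5.1 being used to grade infections and on the rash assumption behind the reading of (d). How many subjects could be affected cannot be worked out, because the protocol gives no incidence for either infection.

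**What to change.** Add one footnote to the three cells of Table 2, for example: *Except herpes zoster or ocular herpes: discontinue study drug at any severity and any cell count (see (c)); see also (d) and (e).*

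Criterion (c) needs no rewording. The cost is one table footnote in the next amendment; procedures, data collection, analysis and sample size are unchanged.

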9.4 Treatments

9.4.1 Treatments Administered

For this study the test drug is E2609 and the control drug is placebo. All study drugs are to be administered orally, QD, with food.

Treatments to be administered in Stage A and Stage B are shown below and in [Figure 1](#).

The 2 highest E2609 doses (15 and 50 mg) taken into Stage B, after the PK/PD and safety review from Stage A, will be used for the mild to moderate AD population in Stage B. (revised per Amendment 01)

- Stage A: 3 doses (5, 15, and 50 mg) of E2609 or placebo
- Stage B, MCI/Prodromal Cohort: 3 doses (5, 15, and 50 mg) of E2609 or placebo
- Stage B, Mild to Moderate AD Cohort: 2 doses (15 and 50 mg) of E2609 or placebo. (revised per Amendment 01)

Study treatment will begin on Day 1 (at the study site) following Randomization and will continue for approximately 78 weeks. Please refer to [Table 7](#) and [Section 9.5.1.4.1](#) for specific information on drug administration on days when PK sampling is to be performed.

Study drug doses will remain the same for each individual subject unless the interim PK/PD analysis determines that an entire dose level requires adjustment ([Section 9.4.4](#)). See

[Section 9.3.3](#) for safety-related discontinuation criteria of study drug. If a subject develops a concurrent illness during the treatment period, the investigator should discuss with the medical monitor on whether dosing with study drug needs to be temporarily suspended. As a general clinical guideline, dosing with study drug may be resumed after resolution or stabilization of the concurrent illness, after discussion with the medical monitor.

